Number (%) of Subjects Who Expired	n (%)	n (%)	n (%)
Number (%) of Subjects Censored	n (%)	n (%)	n (%)
Quartiles [95% CI] (days)			
25 th Percentile	xx (xx.x, xx.x)	xx (xx.x, xx.x)	xx (xx.x, xx.x)
50 th Percentile	xx (xx.x, xx.x)	xx (xx.x, xx.x)	xx (xx.x, xx.x)
75 th Percentile	xx (xx.x, xx.x)	xx (xx.x, xx.x)	xx (xx.x, xx.x)
p-value ^[1]		x.XXXX	x.XXXX
Kaplan Meier Estimate (# at Risk)			
6 Months	x.XXXX (n)	x.XXXX (n)	x.XXXX (n)
12 Months	x.XXXX (n)	x.XXXX (n)	x.XXXX (n)
Range (days)			
Subjects with an Event	xx, xx	xx, xx	xx, xx
All Subjects	xx, xx	xx, xx	xx, xx

^[1] P-value test for treatment difference using log rank test.
path\t_program.sas date time

Programmer Note Tables 11.1.2 will be identical to Table 11.1.1 for the ITT Population.
Programmer Note For censoring rules, see Section 10.2.7 of the Statistical Analysis Plan.

Table 12.1
Rutherford Classification of Disease Severity
Per-Protocol Population

	Placebo (N=)		VM202- 8 mg (N=)		VM202- 16 mg (N=)	
	Result	Change ^[2]	Result	Change ^[2]	Result	Change ^[2]
Baseline^[1]						
N		n xx.x (xx.xx)		n xx.x (xx.xx)		n xx.x (xx.xx)
Mean (SD)		xx.x		xx.x		xx.x
Median		xx, xx		xx, xx		xx, xx
Min, Max						
6 Months						
N		n xx.x (xx.xx)	n xx.x (xx.xx)	n xx.x (xx.xx)	n xx.x (xx.xx)	n xx.x (xx.xx)
Mean (SD)		xx.x	xx.x	xx.x	xx.x	xx.x
Median		xx, xx	xx, xx	xx, xx	xx, xx	xx, xx
Min, Max						
Comparison vs. Placebo						
Model 1^[3]						
LS Means (SE)			xx.x (xx.x)		xx.x (xx.x)	xx.x (xx.x)
LS Mean Differences (SE)					xx.x (xx)	xx.x (xx)
95% CI for LS Mean Differences					(xx.x, x.xx)	(xx.x, x.xx)
Overall p-value for Treatment Differences						
Pairwise p-value vs. Placebo (Dunnett's test)					x.XXXX	x.XXXX
Baseline vs. 6 Months (Paired t-test)		x.XXXX		x.XXXX		x.XXXX
Model 2^[4]						
Overall p-value for Treatment Differences (Jonckherre-Terpstra test)					x.XXXX	x.XXXX
Pairwise p-value vs. Placebo (Wilcoxon Rank Sum test)					x.XXXX	x.XXXX
Baseline vs. 6 Months (Wilcoxon Signed Rank test)		x.XXXX		x.XXXX		x.XXXX

^[1] Baseline defined as the last non-missing value prior to first dose of study drug.

^[2] Change = Change from Baseline

^[3] One-way analysis of variance (ANOVA) with treatment group as a factor.

^[4] Nonparametric tests for differences across a one-way classification of treatment.

path\t_program.sas date time

Programmer Note Repeat for all available time point, 6mo, 9mo and 12mo.

Programmer Note Tables 12.2 will be identical to Table 12.1 for the ITT Population.

Table 13
Study Drug Exposure
Safety Population

	Placebo (N=)	VM202- 8 mg (N=)	VM202- 16 mg (N=)
Day 0			
Dose Administered?			
Yes	n (%)	n (%)	n (%)
No	n (%)	n (%)	n (%)
Zone of Injections ^[1]			
I	n (%)	n (%)	n (%)
II	n (%)	n (%)	n (%)
III	n (%)	n (%)	n (%)
IV	n (%)	n (%)	n (%)
Total Volume Administered per Protocol?			
Yes	n (%)	n (%)	n (%)
No	n (%)	n (%)	n (%)
Duration of Dose Administration (min)			
N	n	n	n
Mean (SD)	xx.x (xx.xx)	xx.x (xx.xx)	xx.x (xx.xx)
Median	xx.x	xx.x	xx.x
Min, Max	xx, xx	xx, xx	xx, xx
Day 14			
Dose Administered?			
Yes	n (%)	n (%)	n (%)
No	n (%)	n (%)	n (%)
Etc.

^[1] Percentage may add up to more than 100% because more than 1 zone can be reported per subject.
path\t_program.sas date time

Programmer Note Repeat for all available time point, Day 14, Day 28, and Day 42.

Table 14
Treatment Emergent Adverse Events by System Organ Class and Preferred Term
Safety Population

System Organ Class / Preferred Term	-Placebo (N=)		VM202- 8 mg (N=)		VM202- 16 mg (N=)	
	Number of Subjects ^[1]	Number of Events	Number of Subjects ^[1]	Number of Events	Number of Subjects ^[1]	Number of Events
Subjects Reporting at Least One Adverse Event	n (%)	n	n (%)	n	n (%)	n
System Organ Class 1	n (%)	n	n (%)	n	n (%)	n
Preferred Term 1	n (%)	n	n (%)	n	n (%)	n
Preferred Term 2	n (%)	n	n (%)	n	n (%)	n
.
System Organ Class 2	n (%)	n	n (%)	n	n (%)	n
Preferred Term 1	n (%)	n	n (%)	n	n (%)	n
Preferred Term 2	n (%)	n	n (%)	n	n (%)	n
Etc.						

^[1] At each level of summation (overall, system organ class, preferred term), subjects reporting more than one adverse event are counted only once.
path\t_program.sas date time

Table 15
Treatment Emergent Adverse Events by Maximum Severity
Safety Population

System Organ Class / Preferred Term	Placebo (N=)			VM202- 8 mg (N=)			VM202- 16 mg (N=)		
	Mild	Moderate	Severe	Mild	Moderate	Severe	Mild	Moderate	Severe
Subjects Reporting at Least One Adverse Event	n (%)	n (%)	n (%)	n (%)	n (%)	n (%)	n (%)	n (%)	n (%)
System Organ Class 1	n (%)	n (%)	n (%)	n (%)	n (%)	n (%)	n (%)	n (%)	n (%)
Preferred Term 1	n (%)	n (%)	n (%)	n (%)	n (%)	n (%)	n (%)	n (%)	n (%)
Preferred Term 2	n (%)	n (%)	n (%)	n (%)	n (%)	n (%)	n (%)	n (%)	n (%)
.									
.									
System Organ Class 2	n (%)	n (%)	n (%)	n (%)	n (%)	n (%)	n (%)	n (%)	n (%)
Preferred Term 1	n (%)	n (%)	n (%)	n (%)	n (%)	n (%)	n (%)	n (%)	n (%)
Preferred Term 2	n (%)	n (%)	n (%)	n (%)	n (%)	n (%)	n (%)	n (%)	n (%)

Etc.

Note: At each level of summation (overall, system organ class, preferred term), subjects reporting more than one adverse event are counted only once using the highest severity.
path\t_program.sas date time

Table 16
Treatment Emergent Adverse Events by Relationship to Study Drug
Safety Population

System Organ Class / Preferred Term	Placebo (N=)		VM202- 8 mg (N=)		VM202- 16 mg (N=)	
	Related ^[1]	Unrelated ^[2]	Related ^[1]	Unrelated ^[2]	Related ^[1]	Unrelated ^[2]
Subjects Reporting at Least One Adverse Event	n (%)	n (%)	n (%)	n (%)	n (%)	n (%)
System Organ Class 1	n (%)	n (%)	n (%)	n (%)	n (%)	n (%)
Preferred Term 1	n (%)	n (%)	n (%)	n (%)	n (%)	n (%)
Preferred Term 2	n (%)	n (%)	n (%)	n (%)	n (%)	n (%)
System Organ Class 2	n (%)	n (%)	n (%)	n (%)	n (%)	n (%)
Preferred Term 1	n (%)	n (%)	n (%)	n (%)	n (%)	n (%)
Preferred Term 2	n (%)	n (%)	n (%)	n (%)	n (%)	n (%)

Note: At each level of summation (overall, system organ class, preferred term), subjects reporting more than one adverse event are counted only once using the closest relationship to study drug.

^[1] Includes all events reported as "Possibly," "Probably," "Definitely" or with missing relationship to study drug.

^[2] Includes all events reported as "Not Related" relationship to study drug.

path\t_program.sas date time

Table 17
Treatment Emergent Serious Adverse Events by System Organ Class and Preferred Term
Safety Population

System Organ Class / Preferred Term	Placebo (N=)		VM202- 8 mg (N=)		VM202- 16 mg (N=)	
	Number of Subjects ^[1]	Number of Events	Number of Subjects ^[1]	Number of Events	Number of Subjects ^[1]	Number of Events
Subjects Reporting at Least One Serious Adverse Event	n (%)	n	n (%)	n	n (%)	n
System Organ Class 1	n (%)	n	n (%)	n	n (%)	n
Preferred Term 1	n (%)	n	n (%)	n	n (%)	n
Preferred Term 2	n (%)	n	n (%)	n	n (%)	n
System Organ Class 2	n (%)	n	n (%)	n	n (%)	n
Preferred Term 1	n (%)	n	n (%)	n	n (%)	n
Preferred Term 2	n (%)	n	n (%)	n	n (%)	n
Etc.						

^[1] At each level of summation (overall, system organ class, preferred term), subjects reporting more than one adverse event are counted only once.
path\t_program.sas date time

Table 18
Hematology - Shift from Baseline
Safety Population
Analyte #1

Time Point	Baseline ^[1]								
	Placebo (N=)			VM202- 8 mg (N=)			VM202- 16 mg (N=)		
	High	Normal	Low	High	Normal	Low	High	Normal	Low
Day 14									
High	n (%)	n (%)	n (%)	n (%)	n (%)	n (%)	n (%)	n (%)	n (%)
Normal	n (%)	n (%)	n (%)	n (%)	n (%)	n (%)	n (%)	n (%)	n (%)
Low	n (%)	n (%)	n (%)	n (%)	n (%)	n (%)	n (%)	n (%)	n (%)
Day 28									
High	n (%)	n (%)	n (%)	n (%)	n (%)	n (%)	n (%)	n (%)	n (%)
Normal	n (%)	n (%)	n (%)	n (%)	n (%)	n (%)	n (%)	n (%)	n (%)
Low	n (%)	n (%)	n (%)	n (%)	n (%)	n (%)	n (%)	n (%)	n (%)
Etc.									

^[1] Baseline defined as the last non-missing value prior to first dose of study drug.
path\t_program.sas date time

Programmer Note Analytes to be shown include Hematocrit, Hemoglobin, RBC, WBC, Platelets, Neutrophils, Lymphocytes, Monocytes, Eosinophils, Basophils, MCV, MCHC, MCH.

Table 19
Serum Chemistry - Shift from Baseline
Safety Population
Analyte #1

Time Point	Baseline ^[1]								
	Placebo (N=)			VM202- 8 mg (N=)			VM202- 16 mg (N=)		
	High	Normal	Low	High	Normal	Low	High	Normal	Low
Day 14									
High	n (%)	n (%)	n (%)	n (%)	n (%)	n (%)	n (%)	n (%)	n (%)
Normal	n (%)	n (%)	n (%)	n (%)	n (%)	n (%)	n (%)	n (%)	n (%)
Low	n (%)	n (%)	n (%)	n (%)	n (%)	n (%)	n (%)	n (%)	n (%)
Day 28									
High	n (%)	n (%)	n (%)	n (%)	n (%)	n (%)	n (%)	n (%)	n (%)
Normal	n (%)	n (%)	n (%)	n (%)	n (%)	n (%)	n (%)	n (%)	n (%)
Low	n (%)	n (%)	n (%)	n (%)	n (%)	n (%)	n (%)	n (%)	n (%)
Etc.									

^[1] Baseline defined as the last non-missing value prior to first dose of study drug.
path\t_program.sas date time

Programmer Note Analytes to be shown include Albumin, Alkaline Phosphate, ALT, AST, Bicarbonate, BUN, Calcium, Chloride, Creatinine, GGT Glucose, LDH, Phosphorus, Sodium, Total Bilirubin, Total Protein, Uric Acid.

Table 20
Vital Signs
Safety Population

Vital Sign	Placebo (N=)		VM202- 8 mg (N=)		VM202- 16 mg (N=)	
	Result	Change ^[2]	Result	Change ^[2]	Result	Change ^[2]
Heart Rate (bpm)						
Baseline ^[1]						
N	n		n		n	
Mean (SD)	xx.x (xx.xx)		xx.x (xx.xx)		xx.x (xx.xx)	
Median	xx.x		xx.x		xx.x	
Min, Max	xx, xx		xx, xx		xx, xx	
Day 0 (Post Dose)						
N	n	n	n	n	n	n
Mean (SD)	xx.x (xx.xx)	xx.x (xx.xx)	xx.x (xx.xx)	xx.x (xx.xx)	xx.x (xx.xx)	xx.x (xx.xx)
Median	xx.x	xx.x	xx.x	xx.x	xx.x	xx.x
Min, Max	xx, xx	xx, xx	xx, xx	xx, xx	xx, xx	xx, xx
Day 14 (Pre- Dose)						
N	n	n	n	n	n	n
Mean (SD)	xx.x (xx.xx)	xx.x (xx.xx)	xx.x (xx.xx)	xx.x (xx.xx)	xx.x (xx.xx)	xx.x (xx.xx)
Median	xx.x	xx.x	xx.x	xx.x	xx.x	xx.x
Min, Max	xx, xx	xx, xx	xx, xx	xx, xx	xx, xx	xx, xx
Day 14 (Post-Dose)						
N	n	n	n	n	n	n
Mean (SD)	xx.x (xx.xx)	xx.x (xx.xx)	xx.x (xx.xx)	xx.x (xx.xx)	xx.x (xx.xx)	xx.x (xx.xx)
Median	xx.x	xx.x	xx.x	xx.x	xx.x	xx.x
Min, Max	xx, xx	xx, xx	xx, xx	xx, xx	xx, xx	xx, xx
Etc.						

^[1] Baseline defined as the last non-missing value prior to first dose of study drug.

^[2] Change = Change from Baseline

path\t_program.sas date time

Programmer Note Repeat for all available time points and vital signs.

Table 21
Retinal Fundoscopy- Shift from Baseline
Safety Population

	Screening/Baseline								
	Placebo (N=)		VM202- 8 mg (N=)		VM202- 16 mg (N=)				
	Normal	Abn, Not CS ^[1]	Abn, CS ^[2]	Normal	Abn, Not CS ^[1]	Abn, CS ^[2]	Normal	Abn, Not CS ^[1]	Abn, CS ^[2]
12 Months									
Right		n			n			n	
Normal	n (%)	n (%)	n (%)	n (%)	n (%)	n (%)	n (%)	n (%)	n (%)
Abnormal, Not Clinically Significant	n (%)	n (%)	n (%)	n (%)	n (%)	n (%)	n (%)	n (%)	n (%)
Abnormal, Clinically Significant	n (%)	n (%)	n (%)	n (%)	n (%)	n (%)	n (%)	n (%)	n (%)
Left		n			n			n	
Normal	n (%)	n (%)	n (%)	n (%)	n (%)	n (%)	n (%)	n (%)	n (%)
Abnormal, Not Clinically Significant	n (%)	n (%)	n (%)	n (%)	n (%)	n (%)	n (%)	n (%)	n (%)
Abnormal, Clinically Significant	n (%)	n (%)	n (%)	n (%)	n (%)	n (%)	n (%)	n (%)	n (%)

Note: In the case of an early withdrawal, the result from the last retinal fundoscopy is considered for the 12 Months visit.

[¹] Abn, Not CS= Abnormal, Not Clinically Significant

[²] Abn, CS= Abnormal, Clinically Significant

path\t_program.sas date time

Table 22
Injection Site Reaction
Safety Population

	Placebo (N=)	VM202- 8 mg (N=)	VM202- 16 mg (N=)
Subject reported an Injection Site Reaction?			
Day 0 (Post-Dose)			
Yes	n n (%)	n n (%)	n n (%)
No	n n (%)	n n (%)	n n (%)
Day14 (Pre-Dose)			
Yes	n n (%)	n n (%)	n n (%)
No	n n (%)	n n (%)	n n (%)
Day14 (Post-Dose)			
Yes	n n (%)	n n (%)	n n (%)
No	n n (%)	n n (%)	n n (%)
Etc.			

path\t_program.sas date time

Programmer Note Repeat for all available time point, Day 28(pre- and post-dose), Day 42(pre- and post-dose), and Day 49(pre- and post-dose).

[figure not shown]
Table 23
Prior and Concomitant Medications
Safety Population

ATC Drug Class / Medication Term	Placebo (N=)	VM202- 8 mg (N=)	VM202- 16 mg (N=)
Subjects Receiving any Concomitant Medications	n (%)	n (%)	n (%)
Drug Class 1	n (%)	n (%)	n (%)
Medication Term 1	n (%)	n (%)	n (%)
Medication Term 2	n (%)	n (%)	n (%)
.	.	.	.
Drug Class 2	n (%)	n (%)	n (%)
Medication Term 1	n (%)	n (%)	n (%)
Medication Term 2	n (%)	n (%)	n (%)
.	.	.	.
Etc.			

Note: At each level of summation (overall, ATC drug class, medication term), subjects reporting more than medication are counted only once.
path\t_program.sas date time

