6. ANALYSIS POPULATIONS

The following subject populations will be used for analysis:

The Intent-to-Treat (ITT) population will include all subjects who were randomized regardless of whether treatment was received. Subjects will be analyzed according to the treatment to which they were randomized.

The Safety population will include all subjects who receive at least one dose of study drug medication and data will be analyzed according to the treatment actually received. The safety analyses will be performed on the Safety population.

The per-protocol (PP) population will include all subjects who received the correct dose of study drug medication, have the 9-month VAS assessment, and do not have any protocol violations or major deviations as determined by Medical Monitoring. The per-protocol population will be determined in a blinded review before database lock. Subjects will be analyzed according to the treatment to which they were randomized. Primary efficacy analyses will be performed on the PP population.

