10.1.2. Imputation Methods of VAS Results for the ITT Population

In order to include all subjects in the ITT population, the following imputation rules will be applied for analysis of the ITT population.

For subjects without the primary efficacy endpoint (VAS change from baseline to 9 months), the following imputation methods will be applied:

- For missing Baseline VAS, assign the VAS score at Screening if the VAS score at Day 0 is missing.
- For missing 9 month VAS, assign the 12 month VAS score if the 9 month VAS is missing.

- For missing 9 month VAS, assign the last reported VAS prior to the 9 month VAS visit if both the 9 month and 12 month VAS assessments are missing.

For subjects who had a major amputation or limb procedure carried out, the following imputation methods will be applied:

- For subjects with a major amputation, assign the post baseline VAS score prior to the amputation.
- For subjects with a limb salvage, assign the post baseline VAS score prior to the intervention.

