10.2. Secondary Efficacy Variables

The analyses for the secondary efficacy variables will be performed based on the Per-Protocol Population and ITT Populations. The secondary efficacy endpoints include:

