10.2.1. VISUAL ANALOGUE SCALE FOR PAIN (VAS)

The VAS measurements, change from baseline and percent change from baseline will be summarized at each visit by treatment arm using the methods described in Section 10.1.

Categorical analysis of VAS measurements will be performed by visit. Each VAS measurement will be assigned to one of the following 4 categories: 0-4 mm, 5-44 mm, 45-74 mm and 75-100 mm. Incidence and percentage of each VAS category will be presented for Baseline and each post baseline visit. Testing for treatment differences versus placebo will be carried out using a CMH test (Row Means Score).

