75-100 mm	n (%)	n (%)	n (%)
Pairwise p -value vs. Placebo [2]		.XXXX	.XXXX
....			

Note: Only subjects with ulcers at baseline are considered for analysis.

[1] Baseline defined as the last non-missing value prior to first dose of study drug.

[2] Pairwise *p*-value tests for treatment group difference using CMH test (Row Mean Scores).

path\t_program.sas date time

Programmer Note Repeat for all available time points, Day14, Day 28, Day 42, Day 90, 6mo, 9mo, and 12mo.

Programmer Note Tables 5.4.2 will be identical to Table 5.4.1 for the ITT Population using imputation rules specified in Section 10.1.2 of the Statistical Analysis Plan.

Table 6.1.1.1
Transcutaneous Oxygen Pressure Assessment- TcPO₂ (mmHg) – Anterior Calf
Per-Protocol Population

	Placebo (N=)		VM202- 8 mg (N=)		VM202- 16 mg (N=)	
	Result	Change ^[2]	Result	Change ^[2]	Result	Change ^[2]
Baseline ^[1]						
N		n		n		n
Mean (SD)		xx.x (xx.xx)		xx.x (xx.xx)		xx.x (xx.xx)
Median		xx.x		xx.x		xx.x
Min, Max		xx, xx		xx, xx		xx, xx
6 Months						
N		n	n	n	n	n
Mean (SD)		xx.x (xx.xx)	xx.x (xx.xx)	xx.x (xx.xx)	xx.x (xx.xx)	xx.x (xx.xx)
Median		xx.x	xx.x	xx.x	xx.x	xx.x
Min, Max		xx, xx	xx, xx	xx, xx	xx, xx	xx, xx
Comparison vs. Placebo						
Model 1 ^[3]						
LS Means (SE)			xx.x (xx.x)		xx.x (xx.x)	
LS Mean Differences (SE)				xx.x (xx)		xx.x (xx)
95% CI for LS Mean Differences				(xx.x, x.xx)		(xx.x, x.xx)
Overall p-value for Treatment Differences						x.XXXX
Pairwise p-value vs. Placebo (Dunnett's test)					x.XXXX	x.XXXX
Baseline vs. 6 Months (Paired t-test)			x.XXXX		x.XXXX	x.XXXX
Model 2 ^[4]						
Overall p-value for Treatment Differences (Jonckherre-Terpstra test)						x.XXXX
Pairwise p-value vs. Placebo (Wilcoxon Rank Sum test)				x.XXXX		x.XXXX
Baseline vs. 6 Months (Wilcoxon Signed Rank test)			x.XXXX		x.XXXX	x.XXXX

^[1] Baseline value is the ratio taken at the Day 0 (Pre-Dose) Visit if the percent difference ($=|Day 0 - Screening|/Screening \times 100\%$) between the ratios taken at the Screening Visit and the Day-0 Visit is $\leq 15\%$. Otherwise, the baseline value is the average of the ratios at Screening and Day 0 Visits.

^[2] Change = Change from Baseline

^[3] One-way analysis of variance (ANOVA) with treatment groups as a factor.

^[4] Nonparametric tests for differences across a one-way classification of treatment.

path\t_program.sas date time

Programmer Note Repeat for all available time points, 6mo, 9mo and 12mo.

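### The shell for the categorical VAS tables (5.4.1 and 5.4.2) restricts a pain analysis to subjects with baseline ulcers, a condition that SAP 10.2 and 10.2.1 do not contain

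*SAP*

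**What the plan says.** SAP 10.2.1 describes the categorical analysis of pain as follows: "Each VAS measurement will be assigned to one of the following 4 categories: 0-4 mm, 5-44 mm, 45-74 mm and 75-100 mm". It continues: "Incidence and percentage of each VAS category will be presented for Baseline and each post baseline visit". Each dose is then compared with placebo by a CMH row mean score test. The section sets no condition on ulcers.

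The populations come from the parent section, SAP 10.2: "The analyses for the secondary efficacy variables will be performed based on the Per-Protocol Population and ITT Populations". SAP section 6 defines the ITT set: "The Intent-to-Treat (ITT) population will include all subjects who were randomized regardless of whether treatment was received". The per-protocol set depends on correct dosing, a 9-month VAS and the absence of violations. Neither definition refers to ulcers.

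In SAP Appendix B, the Table 5.4.1 shell is headed as per-protocol, but the note under it reads "Only subjects with ulcers at baseline are considered for analysis". The programmer note extends the shell to the ITT set: "Tables 5.4.2 will be identical to Table 5.4.1 for the ITT Population using imputation rules specified in Section 10.1.2".

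**The concern.** The shell and the text define different sets of patients for the same table. Programmers usually build from shells, so the restriction may well be applied.

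Protocol 3.3.1 admits Rutherford class 4 or 5, and its criterion 4 can be met by rest pain, ischemic ulcers or small focal gangrene, alone or together. A patient with no ulcer is therefore eligible, and may have entered the trial on pain alone. The note would remove these patients from a pain table.

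Two things are at stake. First, Tables 5.4.1 and 5.4.2 would be labelled per-protocol and ITT but would describe a subgroup that the SAP text never defines, and their counts would not match Tables 5.1 and 5.2 under the same labels. Secondly, if the conflict is noticed only after the codes are unmasked, choosing between the two readings becomes a post hoc choice of population. If programmers instead ignore the note but leave it printed, the output misstates who was analysed.

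**Working it through.** The plan gives no figure for this analysis, so there is none to reproduce. The check is a comparison of texts, followed by simple counts.

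**1. Text against shell**
- SAP 10.2.1 categorises each VAS measurement, without an ulcer condition.
- SAP 10.2 and section 6 give the scope as all per-protocol subjects for Table 5.4.1 and all randomized subjects for Table 5.4.2.
- The Table 5.4.1 shell keeps only subjects with baseline ulcers, and Table 5.4.2 inherits this.

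These cannot both be followed unless every subject in the set has an ulcer, and the inclusion criteria do not require one.

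**2. Shell against its own cross-reference**

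Table 5.4.2 is to use the rules of SAP 10.1.2. That section gives its purpose as "In order to include all subjects in the ITT population". One table cannot fill in missing values so as to keep everybody and also drop everybody without an ulcer.

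**3. Other shells**
- The VAS shells for Tables 5.1, 5.2 and 5.3 do not carry the note.
- Table 9.2.1 (wound healing) carries the identical sentence. There it fits, because only an existing ulcer can heal. That shell also has a row counting subjects with no ulcer at baseline. Table 5.4.1 has no such row, so a reader could not see how many had been left out.
- The VAS subgroups planned in SAP 10.1.1 are sex, diabetes and renal dysfunction. Ulcer status is not among them.

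**4. Who is dropped**

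Listing 26 in the SAP labels Rutherford class 4 as ischemic rest pain and includes both non-healing ulcer and focal gangrene under class 5. The note therefore removes patients with rest pain only and, read literally, class 5 patients with focal gangrene but no ulcer.

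**5. How many tests are affected**

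The shell covers baseline plus seven visits (Days 14, 28, 42 and 90; months 6, 9 and 12), with two pairwise p-values at each. That is 8 × 2 = 16 p-values per table, or 32 over the two tables.

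**6. How many subjects might remain (illustration)**

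SAP section 4 plans 20:20:10, or 50 in all. Let s be the share with a baseline ulcer, assumed equal across arms. The documents do not give s. The number remaining in Table 5.4.2 is 50 × s:
- s = 0.3: 50 × 0.3 = 15 (6:6:3)
- s = 0.5: 50 × 0.5 = 25 (10:10:5)
- s = 0.7: 50 × 0.7 = 35 (14:14:7)

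The per-protocol table would start from whatever smaller number qualifies, which cannot be known in advance.

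**The case against.** The strongest reply is that little depends on this table. The secondary endpoints in protocol 6.2.2 include change in VAS score but not VAS categories, so the categorical analysis is an addition made in the SAP. The primary analysis in SAP 10.1 does not use it. Tables 5.1 to 5.3 carry no ulcer note, so patients without ulcers still count in the main VAS summaries and tests. All of this stands, and it limits the point to one supportive analysis.

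A second reply is that the restriction may have been meant. The SAP does not say whether text or shell governs. The match with Table 9.2.1 makes a copying slip the likeliest explanation, but that is an inference. The contradiction remains on either view: an intended subgroup would need a definition in SAP 10.2.1 and a title that says what it is.

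A reader might also infer a measurable loss of power. With a 20 mm difference (30 − 10, high dose against placebo) and SD 25 from SAP section 4, a two-sided 5% t-test has 51% power at 20 v 10, and 38%, 27% and 17% at 14 v 7, 10 v 5 and 6 v 3. The arithmetic is right, but those inputs describe continuous change in VAS. Table 5.4 tests four ordered categories at each visit by CMH, and the plan gives no category probabilities, so the loss for that test cannot be computed. Nor do the documents support saying that the comparison loses most of its information: that would need fewer than half of the patients to have ulcers.

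**Conclusion.** The point holds as an internal contradiction in one secondary analysis. Followed as written, Tables 5.4.1 and 5.4.2 would tabulate and test pain in an undefined ulcer subgroup under per-protocol and ITT labels. They would omit eligible patients without ulcers and would disagree with Tables 5.1 and 5.2. This rests on the wording alone and needs no assumed ulcer share.

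The size is open. The range of 15 to 35 remaining out of 50 rests on an assumed share of 30% to 70%, the same in each arm, and shows scale only. It might be inferred that the primary pain result is compromised. It is not: the primary ANOVA and Dunnett comparisons and Tables 5.1 to 5.3 are unaffected.

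**What to change.** Delete the note from the shells for Tables 5.4.1 and 5.4.2, so that they cover all per-protocol and all ITT subjects respectively. Keep it in Table 9.2. The cost is one line in a shell, with no change to data collection or to any other analysis.

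If a view of pain in patients with ulcers is wanted, define that subgroup in SAP 10.2.1, including whether focal gangrene without an ulcer counts. Present it in a separately titled table with the number excluded shown, as an addition to the full tables. This costs a short paragraph and one more shell. Either change should be made before the randomization codes are unmasked.

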1.8. STUDY AND DOSE RATIONALE

Based on the promising results seen in the phase I study, two doses (8 mg and 16 mg final VM202 dose) will be tested and compared to placebo injections in this phase II study. Patients will be treated with a final dose of 8 mg VM202, 16 mg VM202 or placebo by intramuscular injections in the affected calf on Day 0, Day 14, Day 28 and Day 42. VM202 will be delivered in a solution of 0.5 mg VM202 / mL.

As there are currently no approved drugs that can reverse CLI and as most patients have exhausted surgical and endovascular intervention options, inducing angiogenesis in the affected limb with VM202 may result in an increase in tissue perfusion, which, in turn improve wound healing, reduce pain and improve limb salvage rates.

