2.2. Secondary Objectives

The secondary objective of the study is to evaluate potential bioactivity of IM administration of VM202 in subjects with CLI, when compared to placebo, on:

- Change in VAS for pain at rest
- Leg ulcer healing (as assessed by ulcer surface area and time to complete healing)
- Hemodynamic assessment (ABI/TBI)
- Tissue oxygenation ($TcPO_2$)
- Incidence and extent of lower leg amputation, limb salvage or other surgical interventions
- VascuQoL
- Perfusion (MRA)

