10.2.7. Amputation and Mortality Rate

The rates of amputation, limb salvage and mortality will be analyzed for all treated subjects per actual treatment using the method for time-to-event variables. The probability of being event-free at 6 and 12 months will be summarized for each treatment arm and compared vs. Placebo using a Log Rank test.

The duration of time to amputation will be defined as the number of days between the day of amputation – the first dose date + 1. If a subject does not report amputation, then the date that the subject will be censored at the date of study discontinuation. If the date of study discontinuation is not available, then the subject's censor date will be the last known visit the subject attended. The same calculation will be repeated for limb salvage and mortality (time to death).

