Programmer Note Tables 10.2, 10.3, 10.4, 10.5 and 10.6 will be identical to Table 10.1 for the other domain scores (Symptom, Pain, Emotional, and Social), Total score and Resting Pain Please make change to the footnote for the score definition accordingly.

Programmer Note Table 10.7 will be identical to Table 10.1 for each individual question.

Table 11.1.1
Amputation– Event Free Probability
Per-Protocol Population

Amputation	Placebo (N=)	VM202- 8 mg (N=)	VM202- 16 mg (N=)
Number (%) of Subjects Who Had Amputation	n (%)	n (%)	n (%)
Number (%) of Subjects Censored	n (%)	n (%)	n (%)
Quartiles [95% CI] (days)			
25 th Percentile	xx (xx.x, xx.x)	xx (xx.x, xx.x)	xx (xx.x, xx.x)
50 th Percentile	xx (xx.x, xx.x)	xx (xx.x, xx.x)	xx (xx.x, xx.x)
75 th Percentile	xx (xx.x, xx.x)	xx (xx.x, xx.x)	xx (xx.x, xx.x)
p-value ^[1]		xxxx	xxxx
Kaplan Meier Estimate (# at Risk)			
6 Months	x.xxxx (n)	x.xxxx (n)	x.xxxx (n)
12 Months	x.xxxx (n)	x.xxxx (n)	x.xxxx (n)
Range (days)			
Subjects with an Event	xx, xx	xx, xx	xx, xx
All Subjects	xx, xx	xx, xx	xx, xx

^[1] P-value tests for treatment difference using log rank test.
path\t_program.sas date time

Programmer Note Tables 11.1.2 will be identical to Table 11.1.1 for the ITT Population.
Programmer Note For censoring rules, see Section 10.2.7 of the Statistical Analysis Plan.

Table 11.2.1
Limb Salvage – Event Free Probability
Per-Protocol Population

Limb Salvage	Placebo (N=)	VM202- 8 mg (N=)	VM202- 16 mg (N=)
Number (%) of Subjects Who Had a Limb Salvage Procedure Performed	n (%)	n (%)	n (%)
Number (%) of Subjects Censored	n (%)	n (%)	n (%)
Quartiles [95% CI] (days)			
25 th Percentile	xx (xx.x, xx.x)	xx (xx.x, xx.x)	xx (xx.x, xx.x)
50 th Percentile	xx (xx.x, xx.x)	xx (xx.x, xx.x)	xx (xx.x, xx.x)
75 th Percentile	xx (xx.x, xx.x)	xx (xx.x, xx.x)	xx (xx.x, xx.x)
p-value ^[1]		x.XXXX	x.XXXX
Kaplan Meier Estimate (# at Risk)			
6 Months	x.XXXX (n)	x.XXXX (n)	x.XXXX (n)
12 Months	x.XXXX (n)	x.XXXX (n)	x.XXXX (n)
Range (days)			
Subjects with an Event	xx, xx	xx, xx	xx, xx
All Subjects	xx, xx	xx, xx	xx, xx

^[1] P-value test for treatment difference using log rank test.

path\t_program.sas date time

Programmer Note Tables 11.1.2 will be identical to Table 11.1.1 for the ITT Population.

Programmer Note For censoring rules, see Section 10.2.7 of the Statistical Analysis Plan.

Table 11.3.1
Mortality – Event Free Probability
Per-Protocol Population

Mortality	Placebo (N=)	VM202- 8 mg (N=)	VM202- 16 mg (N=)

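### The SAP's limb-salvage tables count only a limb-salvage procedure as the event, so a leg amputated without one never counts as a failure and more amputations can raise the limb-salvage result

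*SAP*

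**What the plan says.** SAP 2.2 includes limb salvage among the bioactivity measures: "Incidence and extent of lower leg amputation, limb salvage or other surgical interventions". SAP 5.2 assigns it to Kaplan-Meier estimation and the log-rank test. SAP 10.2.7 compares each VM202 arm with placebo and summarises event-free probabilities at 6 and 12 months.

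The event appears only in the SAP Appendix B layout for Table 11.2.1, whose single event row is "Number (%) of Subjects Who Had a Limb Salvage Procedure Performed". The programmer note there says "For censoring rules, see Section 10.2.7 of the Statistical Analysis Plan".

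Section 10.2.7 writes its censoring rule for amputation: "If a subject does not report amputation, then the date that the subject will be censored at the date of study discontinuation". The fallback is "If the date of study discontinuation is not available, then the subject's censor date will be the last known visit the subject attended". It then adds: "The same calculation will be repeated for limb salvage and mortality (time to death"). It does not say what amputation does to the limb-salvage curve.

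The SAP never defines limb salvage. Its imputation rules treat it as an intervention, listed apart from major amputation, for example in 10.1.2: "For subjects with a limb salvage, assign the post baseline VAS score prior to the intervention". Protocol 1.8 uses the phrase in the opposite sense, as a benefit: the treatment may "reduce pain and improve limb salvage rates".

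**The concern.** A patient who loses the treated leg without an earlier procedure can no longer have a salvage procedure on it. Applied as written, the rule makes that patient a non-event who stays in the risk set. The Kaplan-Meier estimate of limb-salvage event-free probability then includes lost legs in its numerator.

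This can mislead in both directions. More amputations can make an arm look better on limb salvage. A treatment that keeps legs in place leaves more of them exposed to a later procedure, and can look worse. The title adds to this, because a reader with the protocol's usage in mind will take a high value to mean legs kept. Limb salvage has two tables, a figure and its own p-values against placebo, so it can be quoted apart from the amputation results.

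**Working it through.** The documents state no limb-salvage figure, so there is none to reproduce. All rates and counts below are assumptions.

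**Inputs.** Event and censoring rule as in Table 11.2.1 and SAP 10.2.7. Arm sizes of 20, 20 and 10 from SAP 4. Assumed: constant hazards, follow-up to 12 months with no other exits, the same 12-month procedure risk *p* in both arms for legs still in place, and 12-month amputation risk *a* of 10% in one arm and 40% in the other.

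**Formulas.** Procedure hazard λp = −ln(1−p); amputation hazard λa = −ln(1−a).
- Procedure before amputation by 12 months: λp/(λp+λa) × (1 − exp(−(λp+λa))).
- Table 11.2.1 event-free probability: 1 minus that.
- Leg kept and no procedure: exp(−(λp+λa)) = (1−p)(1−a).

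**p = 20%.** λp = 0.2231.
- a = 10%: λa = 0.1054. Procedure first = 0.2231/0.3285 × 0.28 = 0.190. Event-free 81.0%. Leg kept, no procedure: 0.8 × 0.9 = 72%.
- a = 40%: λa = 0.5108. Procedure first = 0.2231/0.7340 × 0.52 = 0.158. Event-free 84.2%. Leg kept, no procedure: 0.8 × 0.6 = 48%.

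The difference between the two measures is the amputees counted as event-free: 81.0 − 72 = 9.0 points in the first arm and 84.2 − 48 = 36.2 points in the second.

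**Other procedure risks.**

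| p | Table event-free, a = 10% / 40% | Leg kept, no procedure |
|---|---|---|
| 10% | 90.5% / 92.1% | 81% / 54% |
| 20% | 81.0% / 84.2% | 72% / 48% |
| 30% | 71.4% / 76.2% | 63% / 42% |

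The direction is the same in each row.

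**Effect on the test.** In simulations with p = 20%, 20 patients at a = 40% and 10 patients at a = 10%, the two-sided log-rank test at 0.05 favoured the high-amputation arm in about 5.5% of runs. With equal amputation the figure was about 3.4%. At p = 10% and 30% the excess was also about 2 points.

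**Alternative handling of amputation.**
- *Competing event.* The first formula above is already the cumulative incidence of procedures with amputation as a competing event. With full follow-up this choice returns the same 81.0% and 84.2%.
- *Censoring at amputation.* With equal procedure hazards both arms become exp(−λp) = 80%. The tilt goes, but the curve still says nothing about lost legs. It can still run against limb retention where salvage is attempted less often in one arm. Take assumed counts of 8 amputations and 1 procedure in 20 active patients, and 1 amputation and 4 procedures in 10 placebo patients, in different patients. The SAP rule gives 95.0% against 60.0% event-free (p = 0.014), and censoring at amputation gives 93.8% against 57.1% (p = 0.029). With amputation as the event, the figures are 60.0% against 90.0% (p = 0.11). With either as the event, they are 55.0% against 50.0% (p = 0.80).

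**The case against.** The strongest answer is that the SAP uses the term consistently for a procedure and the row label says so. Amputation has its own Kaplan-Meier table and log-rank test in Table 11.1.1, and its own Figure 1. Protocol 6.2.2 lists the major amputation rate, not limb salvage, as a secondary endpoint. The protocol's contrary usage is in rationale text, not in an endpoint definition. On this view a clearer title is enough. All of these facts stand, and they limit the harm. They do not change what a tested limb-salvage p-value measures when it is quoted alone.

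The size is also open to challenge. At equal procedure risk the shift is 84.2 − 81.0 = 3.2 points, less than one patient in an arm of 20 (0.032 × 20 = 0.64). The p = 0.014 in the count example comes largely from the assumed gap in procedures, 1 of 20 against 4 of 10, so it illustrates what can happen and is not an expected result.

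Two stronger readings are tempting. A reader might infer that amputees are never censored and are formally scored as successes. The documents do not support that: 10.2.7 censors everyone without the event at discontinuation or last visit, the table has a row for censored subjects, and an amputee who leaves the study leaves the risk set then. A patient with a procedure before the amputation does count as an event. That amputees stay at risk follows from carrying the amputation rule over; no sentence says it of them. It is a fair inference, since Protocol 3.5.2 does not name amputation as a reason to discontinue and Protocol 4.2.10 provides a TcPO₂ value for sites lost to amputation.

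A reader might also infer that a fourfold difference in amputation is to be expected. Protocol 1.3.3 gives 45% one-year amputation-free survival and about 25% mortality, which leaves about 30% alive after amputation in CLI generally. It supports neither the 40% level nor any difference between arms, and the trial excludes patients who will need amputation within 4 weeks.

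**Conclusion.** The point holds as one of event definition. As written, an amputation without an earlier procedure is never a limb-salvage event, so at equal procedure risk the reported event-free probability rises with the amputation rate. On the assumed rates the shift is about 2 to 5 points in the wrong direction, while the share with the leg kept and no procedure falls by 21 to 27 points. The false signal added to the log-rank test is about 2 percentage points. These sizes rest on constant hazards, equal procedure risk, full follow-up and assumed rates; the direction does not depend on which of the three procedure risks is used.

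The documents do not support saying that lost legs are hidden from the report or that the trial's main conclusions are affected. Amputation is reported separately, and limb salvage is an SAP bioactivity measure outside the protocol's endpoint list. The exposure is a misleading limb-salvage result read without Table 11.1.1. The change is worth making before database lock.

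**What to change.** In SAP 10.2.7, Tables 11.2.1 and 11.2.2 and Figure 2:

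- Define a limb-salvage procedure, and define the tested event as the first of major amputation of the treated leg or a limb-salvage procedure on that leg.
- Title the outputs *Freedom from major amputation or limb-salvage procedure*, and run the log-rank test on that event.
- Show the two components as descriptive rows.
- If a procedure-only curve is kept, title it *Freedom from limb-salvage procedure*, present it beside the amputation incidence, and do not use it as the limb-salvage comparison. Censoring at amputation, or treating amputation as a competing event, is not enough by itself.

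The cost is SAP wording and recoding of dates. Amputation dates are already needed for 10.2.7, and Listing 39 holds procedure dates, with the leg for peripheral vascular procedures. The downside is that the composite mixes events of different severity, which is why the components must be shown.
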